### **5.1. Summary of Study Design**

The study is a randomized controlled trial, where subjects will be stratified by gender and then randomized 1:1 to the intervention or control arm, as gender has a significant impact on cardiovascular risk, and hence outcomes of MACE.

## **6. METHODS AND ASSESSMENTS**

This is a randomized controlled trial; involving patients aged 21 years and above with low risk chest pain. Patients enrolled will be stratified by gender and then randomized 1:1 into either the intervention arm (CPC) or control arm (usual care). Randomization will be done via an online randomization generator. Recruitment will take place from Sunday 0800 hours to Thursday 2359 hours as inpatient cardiac evaluation investigations such as stress tests and CTCA are only available during weekdays, hence limiting the utility of the ED observation unit on weekends. Those under the intervention arm will receive the Chest Pain Choice visual aid prior to discussion with their primary physician regarding disposition. Data will be collected regarding the patients' age, demographics, past medical history and co-morbidities, cardiovascular risk factors, current medications, variables regarding their current visit such as vital signs, symptoms, laboratory results and electrocardiogram results, treatment received at the emergency department, eventual disposition and downstream cardiac test results if any. In addition to this, patients will answer a questionnaire which will assess patient knowledge, perceptions regarding the information received during consultation, patient satisfaction, as well as the Trust in Physician scale (a tool that assesses interpersonal trust in a patient-physician relationship) and the Decisional Conflict scale (an established tool that assesses personal perceptions regarding decision-making). Please see the data collection form and the patients' questionnaires in Appendix 2.

After discussion between the patient and his/her attending physician, patients will either be discharged from the emergency department with or without outpatient tests to evaluate their cardiac function (e.g. stress tests, CTCA) and/or outpatient Cardiology appointment or admitted to the ED observation unit for further observation and serial troponin testing, whereby further investigations for cardiac evaluation (e.g. stress tests, CTCA) may or may not be done or planned, at the discretion of the attending physician. There is variability in what is considered standard care, as it is dependent on several factors such as the patient's social set-up, availability of inpatient cardiac evaluation, etc., and hence standard care will not be strictly defined.

The patients in both groups will be assessed regarding their pre- and post-consultation knowledge as well as satisfaction during this visit by standardized questionnaires. The patients will be followed up at 60 days to find out if they had MACE, ED re-attendances, as well as whether further tests for cardiac evaluation were done. This will be done via a review of their electronic medical records or via telephone contact if electronic medical records are not available. A MACE is defined as all-cause mortality, myocardial infarction or coronary revascularisation.

## **6.1. Randomisation and Blinding**

Subjects will be stratified by gender and then randomized 1:1 to either the control arm or the intervention arm by the means of a computer program. Allocation will be done after recruitment via the means of sealed, opaque envelopes. The primary physician, study team and patient will not be blinded, as blinding is not possible. However, as the outcomes are objective, the risk of bias is minimal.

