#### **b. Rationale for Study Population**

The target population is that of adults aged 21 years and above who present to ED with chest pain that is considered low risk based on the HEART score (HEART score 0-3). The HEART score is a validated scoring system for patients aged 21 years and above who present with

symptoms suggestive of Acute Coronary Syndromes. The HEART score assigns different points for various features in the patient's history, ECG features, age group, presence of risk factors, and initial troponin level, in order to generate a score that corresponds to a range of percentages for the risk of 6-week MACE. Patients with a HEART score of 0-3 correspond to a 6-week MACE risk of 0.9-1.7%. Since the risk of 6-week MACE is low in these patients, outpatient follow-up and cardiac testing for underlying coronary artery disease can be considered instead of ED observation unit admission. This is also in keeping with current institutional practices.

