## **5. STUDY DESIGN**

This is a randomized controlled trial where subjects are stratified by gender and then randomized 1:1 to the intervention (CPC) or control arm (usual care). The patient, attending physicians, and study team will not be blinded. Study recruitment will take approximately 12 months. Subjects are only directly involved during their ED visit, and will not be required to

participate in further follow-up sessions. Subjects will be followed up at 60 days by a review of their electronic medical records or via telephone only if no electronic records are available.

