### *c. Post Study Follow up and Procedures*

The subjects will then be followed up at 60 days for 30-day and 60-day MACE, repeat ED attendance, and subsequent cardiac testing performed via a review of electronic medical records or contact via telephone if electronic medical records are not available. No other study visits are required.

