## **10. ETHICAL CONSIDERATIONS**

### **10.1. Informed Consent**

Informed consent will be taken after initial assessment and stabilization by the primary physician, and only after initial serum troponin and ECG results are released. If found suitable for the study, the patients will first be approached by their own treating physicians to participate in the project during their visit to the emergency department for consent to be referred to the study team. The investigators of the study will then obtain consent from the patients for the study.

The study team may also recruit patients where the attending physician is part of the study team, and the participant may share a dependent relationship with the study team. In order to prevent coercion or undue influence, participation is voluntary and the research participants may withdraw from the study at any time without any compromise in their medical care. For participants who are patients of the study team, their decision to participate in the research study will not affect the standard of care provided to them. Where possible, the informed consent process will be conducted by a qualified study team member, delegated by the PI, who is not involved in the primary care for the research participant.

The research participants will be recruited by face-to-face contact when they are in the emergency department. The subject will have sufficient time to consider his/her participation in the study, and have the option of discussing their participation with family members if needed. The consent process will take place in the emergency department within the patient's cubicle. There will be privacy to the patient and a non-threatening, quiet environment for the patient to assess the risks and benefits afforded to him/her with participation of the study. In situations where there is a dependent patient-doctor relationship, it would be emphasised that participation is entirely voluntary and there will be no negative consequences from possible refusal or withdrawal from the study. They will also be given ample time to read through the patient information sheet and decide without any influence or coercion.

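### Section 6.1 leaves the whole study team unblinded, but its reason fits only the patient and treating physician: the day-60 review can be at least partly masked at little cost

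*Combined protocol and SAP*

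**What the plan says.** Section 5 states: "The patient, attending physicians, and study team will not be blinded". Section 6.1 repeats this with a reason, "The primary physician, study team and patient will not be blinded, as blinding is not possible", and adds a defence: "However, as the outcomes are objective, the risk of bias is minimal".

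Subjects are "followed up at 60 days by a review of their electronic medical records or via telephone only if no electronic records are available" (section 5). Section 6.2 c lists what is collected besides 30- and 60-day MACE: "repeat ED attendance, and subsequent cardiac testing performed via a review of electronic medical records or contact via telephone". Section 6 gives the composite: "A MACE is defined as all-cause mortality, myocardial infarction or coronary revascularisation". It gives no diagnostic criteria for MI.

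No section says who carries out the 60-day review. Section 7.3 gives data and safety monitoring to the principal investigator and the study team. Section 10.1 adds: "The study team may also recruit patients where the attending physician is part of the study team". No masked assessor and no event adjudication is described.

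**The concern.** Blinding is impossible for the two parties who hold the index-visit discussion, because one arm has the visual aid and the other does not. That reason does not carry over to a record review two months later, yet the protocol applies it to the whole team.

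Two steps in the follow-up leave room for judgement. The first is whether a troponin result, a discharge note or a telephone account amounts to an MI when no criteria are written down. The second is how hard the reviewer searches, and when the records are taken to be unavailable so that a call is made. Knowledge of the arm can influence both.

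This touches the safety side of the trial's question. Section 1.2 a asks whether the aid can reduce admissions safely, and section 2.4 b names higher MACE in the intervention arm as a potential risk. When so few events are expected, one differently judged record changes the picture.

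**Working it through.** **Inputs**

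- Arm size: 82 per arm (164 in total, section 9.1), or 100 per arm (200 enrolled, section 3.1, at 1:1).
- MACE risk, section 1.2 b: "Patients with a HEART score of 0-3 correspond to a 6-week MACE risk of 0.9-1.7" per cent. This is a 6-week figure. None is given for 30 or 60 days, so using it for either is an assumption.
- Interim look at 50% of recruitment (sections 7.1 and 9.2): 41 to 50 per arm.

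**The plan's own figure.** Section 9.1 gives no control admission rate. Assuming 40% against 20%, with pooled variance, two-sided 0.05 and 80% power:

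n = [1.96 × √(2 × 0.3 × 0.7) + 0.842 × √(0.4 × 0.6 + 0.2 × 0.8)]² / 0.2² = (1.270 + 0.532)² / 0.04 ≈ 81.2, so 82 per arm.

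The stated size is reproduced under that assumption (80% against 60% also gives 82). For control rates from 20% to 100% the result runs from 35 to 97 per arm. Masking the follow-up does not change the sample size.

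**Size of one event and events expected** (one event = 1/n; expected events = n × 0.009 to n × 0.017)

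| Arm size | One event | Expected per arm | Expected, both arms |
|---|---|---|---|
| 82 | 1.22 points | 0.74-1.39 | 1.48-2.79 |
| 100 | 1.00 point | 0.90-1.70 | 1.80-3.40 |
| 41 (interim) | 2.44 points | 0.37-0.70 | 0.74-1.39 |
| 50 (interim) | 2.00 points | 0.45-0.85 | 0.90-1.70 |

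The interim rows assume that follow-up is complete for everyone counted. At full size one event is 1/1.39 = 0.72 to 1/0.74 = 1.36 times an arm's expected count (n = 82), or 1/1.70 = 0.59 to 1/0.90 = 1.11 times (n = 100). That is about one arm's expected risk, not the whole trial's.

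**Can one event trigger action?** For k events against 0, the uncorrected chi-square is 2nk/(2n − k), to be compared with 3.84.

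- n = 82, k = 1: 164/163 = 1.01.
- n = 82, k = 3: 492/161 = 3.06.
- n = 82, k = 4: 656/160 = 4.10, p = 0.043.
- n = 41, k = 4: 328/78 = 4.21, p = 0.040.
- n = 100, k = 4: 800/196 = 4.08, p = 0.043.

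Fisher's exact test needs 6 against 0 (p between 0.026 and 0.029 for 41 to 100 per arm). So one extra event on an even split is far from significance.

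**The safety passages side by side**

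- Section 3.5 says the study may be continued when MACE is shown to be increased.
- Section 7.1 has an increase at the interim look reported to the review board, with no threshold.
- Section 7.3 stops the study on a shown increase, with no threshold.
- Section 9.2 stops it on a significant increase.

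One event could meet the wording of 7.1 and 7.3. From an even split it could not meet that of 9.2.

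**The case against.** The protocol's defence is that the outcomes are objective, and much of that stands. Death and revascularisation leave little to judge. Re-attendance is listed without restriction by cause, and downstream evaluation is named as stress tests or coronary CT, so both are mostly facts of record. Telephone contact is only a fallback. What remains is MI without criteria, and completeness of search. The defence also cannot cover the satisfaction, Trust in Physician and Decisional Conflict questionnaires in section 6, which unblinded patients complete. Masking the follow-up does not help those either.

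Masking will be imperfect. Later notes may mention the aid, and a patient on a call may reveal the arm. Coding the data (sections 8.2 and 10.3) separates identifiers from data. It does not hide the arm, and a record reviewer needs identifiers. These points show that the gain is partial, not that it is absent.

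A reader might infer that treating physicians classify their own patients' outcomes. The documents do not say so: section 10.1 concerns recruitment, and the reviewer is simply not named. A reader might also infer that a single judgement decides the safety result. That fails under section 9.2, as shown above, unless the split is already lopsided.

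A tempting way to strengthen masking is to read only entries after the index visit. That would add a bias. Section 6 sends some patients to the observation unit for serial troponins, and an MI found there could be dropped. If the hypothesis is right, most such losses would be in the control arm. The restriction is also unnecessary, because patients in both arms can be admitted and disposition does not disclose the arm.

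**Conclusion.** The point holds in a limited form and should be acted on. The stated impossibility is true of the patient and treating physician, and too broad for the day-60 reviewer. The bias at risk lies mainly in MI classification and in the thoroughness of the search. One misclassified event is 1.0-1.2 points, against 0.7-1.7 events expected per arm and 1.5-3.4 in the trial. This rests on applying the 6-week risk to the 30- and 60-day outcomes and on equal risk in both arms.

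Two further inferences are not supported. Nothing in the documents shows that masking is free; it is cheap, but the work must be reallocated. Nor does it protect the primary outcome, because the disposition at the index visit is decided by an unblinded patient and physician.

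**What to change.** In sections 5, 6.1 and 6.2 c:

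1. Limit the statement that blinding is impossible to the patient and the treating physician.
2. Have the 60-day review and any call done from a list without the arm, by an existing team member who neither treated nor enrolled that subject.
3. Count MACE in both arms from randomisation, including any observation-unit stay, using one MI definition written down in advance.
4. Merge the arm in only after classification is locked, at the interim look as well as at the end.
5. Limit the claim that outcomes are objective so that it does not cover the questionnaires.

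Separately, reconcile sections 3.5, 7.1, 7.3 and 9.2 on what follows from an increase in MACE.

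Cost: about a paragraph of protocol text, an arm-free work list and an MI definition. Sample size is unchanged and no additional assessor is needed. The downside is that reviews must be shared out among team members, many of whom will also be enrolling. Section 10.1 already asks for a similar separation at consent, where possible. The protocol should acknowledge that masking will be incomplete; recording when the reviewer learned the arm would show by how much.

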### **2.2. Primary Objectives**

1. We aim to evaluate if shared decision-making with patients using the Chest Pain Choice (CPC), a visual decision aid tool, will reduce admissions to the ED observation unit among patients with low-risk chest pain at the index visit to the emergency department.

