The PI and co-investigators will obtain consent from the subjects. A team log will be kept to identify the members as well as their responsibilities within the study. There will not be recruitment of non-English speakers, children, illiterate or non-writing individuals, as the study precludes that only English-literate subjects aged 21 years and above will be able to be recruited. Appendix 3 includes the informed consent form that will be used during the study.

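### Does the claim in section 6.1 that the outcomes are objective leave the primary result exposed to unblinded or investigator-attended admission decisions?

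*Combined protocol and SAP*

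**What the plan says.** Section 6.1 states: "The primary physician, study team and patient will not be blinded, as blinding is not possible". It then concludes: "However, as the outcomes are objective, the risk of bias is minimal". No outcome is exempted.

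Section 2.2 makes the primary question whether the aid "will reduce admissions to the ED observation unit among patients with low-risk chest pain at the index visit to the emergency department". Section 6 describes how that outcome arises: "After discussion between the patient and his/her attending physician, patients will either be discharged from the emergency department"; the alternative is admission to the observation unit. On the comparator it says that care varies and "hence standard care will not be strictly defined". Section 6 also lists questionnaires on perceptions and satisfaction, a trust scale and a decisional-conflict scale.

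Section 10.1 says: "The study team may also recruit patients where the attending physician is part of the study team". Its safeguard applies only when feasible and concerns who takes consent: "informed consent process will be conducted by a qualified study team member, delegated by the PI, who is not involved in the primary care". On membership it adds: "A team log will be kept to identify the members as well as their responsibilities within the study".

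Section 9.2 plans an intention-to-treat analysis with chi-square, Mann-Whitney and t tests, and an interim look at MACE. It plans no analysis by attending.

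**The concern.** Objectivity of an outcome protects against misrecording. It does not protect against influence on the decision being recorded. An admission is easy to verify in the chart, yet in this trial it follows a conversation between two people who both know the arm, with no fixed admission rule. The self-report scales have neither kind of protection.

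The sharper worry is role overlap. A changed conversation is the aid's intended mechanism. An investigator who knows the hypothesis and helps decide the primary outcome is not part of the intervention. The safeguards in section 10.1 deal with consent and voluntariness and do not reach disposition. If admissions fell, a reader might ask whether the fall also held among subjects whose attending was outside the study team, and section 9.2 does not pre-specify an answer. At stake is how far a positive primary result can be credited to the aid.

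**Working it through.** **Which outcomes the sentence fits**

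- *Occurrence of admission, death or ED re-attendance:* objective as to recording, mostly from electronic records, with telephone contact only where records are lacking.
- *Decision to admit:* a judgement by unblinded people. Recording is objective; the decision is open to influence.
- *Revascularisation and later cardiac tests:* recorded events, but also products of clinical decisions.
- *Perceptions, satisfaction, trust, decisional conflict:* self-reports.
- *Knowledge:* a questionnaire measure. It may be scored against correct answers; Appendix 2 is not available to check.

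So the sentence is true of part of the list only.

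**The plan's own figure**

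Section 9.1 gives 82 per arm, 80% power, a 20-point absolute difference and two-sided alpha of 0.05, but no control rate. Assume 40% v 20%, with mean 30%:

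n = [1.96·√(2·0.3·0.7) + 0.8416·√(0.4·0.6 + 0.2·0.8)]² / 0.2² = [1.270 + 0.532]² / 0.04 = 81.2, rounded up to 82.

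The stated figure is reproduced. 80% v 60% gives the same number.

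**What an analysis excluding study-team attendings could show**

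Half-width = 1.96·√[(p1(1−p1) + p2(1−p2))/n]. At 40% v 20% and n = 82 this is 1.96·√(0.40/82) = 13.7 points. The excluded share is an assumption. The totals are the minimum of 164 (section 3.6) and the planned 200 (section 3.1).

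| Total | Excluded | n per arm | Half-width (points) | Power for 20 points |
|---|---|---|---|---|
| 164 | 0% | 82 | 13.7 | 80% |
| 164 | 10% | 73.8 | 14.4 | 76% |
| 164 | 30% | 57.4 | 16.4 | 65% |
| 200 | 0% | 100 | 12.4 | 88% |
| 200 | 10% | 90 | 13.1 | 84% |
| 200 | 30% | 70 | 14.8 | 74% |

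With 30% excluded and control rates of 30% to 60%, the half-width for a 20-point difference runs from 14.2 to 17.9 points at 164 and from 12.8 to 16.2 at 200. At 60% v 40%, power is 57% and 66%. For an observed 10-point fall (40% v 30%) with 30% excluded, the intervals are 10 ± 17.4 (−7.4 to 27.4) at 164 and 10 ± 15.7 (−5.7 to 25.7) at 200.

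**Difference in effect between team and non-team attendings**

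Half-width = √(hw_non-team² + hw_team²), with 40% v 20% in both groups. With 30% team-attended at 164: √(16.4² + 25.0²) = 29.9 points. With 10% team-attended: √(14.4² + 43.3²) = 45.6. At 200 the values are 27.1 and 41.3. No plausible difference could be detected.

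**How much bias the overlap could cause**

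The documents give neither the share of subjects affected nor the shift in decisions. As an illustration, suppose the aid has no effect, the control rate is 50%, there are 82 per arm, and only team attendings admit fewer intervention patients, by 20 points. The overall shift is share × 20 points, and the chance of a two-sided significant result becomes:

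- 10% of subjects: 2-point shift, 5.8%
- 25% of subjects: 5-point shift, 9.8%
- 50% of subjects: 10-point shift, 25%

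The effect is small unless the overlap is common and the shift large.

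**The case for a change.** The strongest case for acting is that it would be cheap. It needs one reworded sentence, at most one data field completed before the envelope is opened, and one secondary analysis. Because attending status would be fixed before allocation, the restricted comparison would stay randomised. At 40% v 20% and with up to 30% excluded, the interval around an observed 20-point fall excludes zero. Sealed envelopes limit selection but do nothing once the arm is known. If unblinded decisions in general lowered intervention-arm admissions by 5 points with no true effect, the false-positive rate at 82 per arm would rise from 5% to about 10–12% for control rates of 30% to 80%. Minimal is therefore an unsupported word.

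Much of this stands. The inference from objective to minimal does not hold for the admission decision or the self-reports. It does not make the plan defective, for four reasons.

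1. The general 5-point shift is not what the proposed exclusion addresses. The remaining attendings are also unblinded, the self-reports are untouched, and carry-over by physicians who treat both arms, which would bias towards no difference, remains.
2. A different result among team attendings could reflect familiarity with the aid, so the exclusion would not isolate bias. With 65% power, a real 20-point effect would miss significance about one time in three and might be misread as evidence of bias.
3. Section 10.1 describes the ordinary route as the treating physician approaching the patient and referring to the study team. The overlap is an additional permission and is never quantified.
4. The question is not closed off afterwards. Team members are logged, section 12 retains source documents, and the Appendix 2 form, which is not available here, may already name the attending. What is missing is pre-specification.

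**Conclusion.** The sentence in section 6.1 overreaches and is best read as a statement about ascertaining recorded events. That is a matter of wording. Correcting it would alter no analysis, decision rule or result, and the facts a reader needs in order to judge bias are already disclosed: no blinding, undefined usual care, and attendings who may be investigators. For a decision aid, an open-label comparison with a disposition outcome is a fair trade-off.

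The sensitivity analysis by attending status is optional, and statisticians could reasonably differ on adding it. Its yield ranges from almost nothing, if few attendings are team members, to an estimate with a half-width of about 14 to 18 points at 164 subjects with 30% excluded. It cannot test whether the effect differs by attending status (half-width about 27 to 46 points across the cases shown). The intention-to-treat chi-square remains the right primary analysis either way.

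These figures rest on assumed admission rates, on assumed team-attended shares of 0% to 30% for precision and 10% to 50% for the bias illustration, and on a pooled two-sided test. The actual share, and the size and direction of any bias, cannot be found from the documents.
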